9.3. Statistical Analyses

The SAP will be developed and finalized before any analyses are performed and will describe the analyses and procedures for accounting for missing, unused, and spurious data. This section is a summary of the planned statistical analyses of the primary and secondary endpoints.

9.3.1. General Considerations

Endpoints will be reported and analyzed according to the hepatic function group that participants fall into based upon their Child-Pugh score at screening.

9.3.1.1. Analyses for PK Endpoints

Natural log-transformed PK parameters (AUC_{inf}, C_{max}, and AUC_{last}, as data permit) will be analyzed using an ANOVA model including hepatic function group as fixed effect. Estimates of the adjusted means and of the adjusted mean differences (Test-Reference) with their corresponding 90% CIs will be obtained before being exponentiated to provide estimates of the adjusted geometric means and of the ratio of adjusted geometric means (Test/Reference).

9.3.2. Primary Endpoint(s) Analysis

9.3.2.1. Definition of Endpoint(s)

The plasma PK parameters for PF-07923568 following single dose administration will be derived from the concentration-time profiles as detailed in Table 4. Actual PK sampling times will be used in the derivation of PK parameters. In the case that actual PK sampling times are not available, nominal PK sampling time will be used in the derivation of PK parameters.

Table 4. Plasma PK Parameters

| Parameter | Definition | Method of Determination |
|----------------------|---|--|
| AUC _{last} | Area under the plasma concentration-time profile from time zero to the time of the last quantifiable concentration (C _{last}) | Linear/Log trapezoidal method. |
| AUC _{inf} * | Area under the plasma concentration-time profile from time zero extrapolated to infinite time | AUC _{last} + (C _{last} * / k _{el}), where C _{last} * is the predicted plasma concentration at the last quantifiable time point estimated from the log-linear regression analysis. |
| C _{max} | Maximum plasma concentration | Observed directly from data. |
| T _{max} | Time for C _{max} | Observed directly from data as time of first occurrence. |

| | | |
|-------------|---------------------------------|---|
| $t_{1/2}^*$ | Terminal half-life | $\text{Log}_e(2)/k_{el}$, where k_{el} is the terminal phase rate constant calculated by a linear regression of the log-linear concentration-time curve. Only those data points judged to describe the terminal log-linear decline will be used in the regression. |
| CL/F^* | Apparent clearance | Dose/ AUC_{inf} . |
| V_z/F^* | Apparent volume of distribution | Dose/($AUC_{\text{inf}} \cdot k_{el}$). |

* as data permit

The plasma concentrations of sisunatovir will be listed and descriptively summarized by nominal PK sampling time and treatment. Individual participant and summary profiles (mean and median plots) of the plasma concentration-time data will be plotted by treatment using actual and nominal times, respectively. Mean and median profiles will be presented on both linear and semi-log scales.

Data permitting, the PK parameters listed in [Table 4](#) will be summarized descriptively by treatment.

9.3.2.2. Main Analytical Approach

The effect of varying degrees of hepatic impairment on PK parameters will be assessed by constructing 90% CIs around the estimated difference between each of the Test (hepatic impaired) groups and the Reference (without hepatic impairment) group. A one-way ANOVA will be used to compare the natural log transformed PF-07923568 AUC_{inf} , C_{max} , and AUC_{last} , as data permit, for each of the hepatic impairment groups (Test) to the group without hepatic impairment (Reference). Estimates of the adjusted mean differences (Test /Reference), and corresponding 90% CIs, will be obtained from the model. These will be exponentiated to provide estimates of the ratio of adjusted geometric means (Test/Reference) and 90% CIs for the ratios.

Individual PF-07923568 concentrations will be listed and summarized descriptively by nominal PK sampling time and hepatic function group. Individual participant and summary profiles of the concentration-time data (using actual and nominal times, respectively) will be plotted by hepatic function group for total plasma PF-07923568.

Box and whisker plots for individual PK parameters (AUC_{inf} , AUC_{last} , and C_{max} , if data permit) will be constructed by hepatic function group and overlaid with geometric means. PK parameters of PF-07923568 will be summarized descriptively by hepatic function group.

9.3.2.3. Supplementary Analyses

Additional analysis using linear regression may be used to analyze the potential relationship between appropriate PK parameters (eg, AUC_{inf} , AUC_{last} , C_{max} , if data permit) and hepatic function (eg, serum albumin concentration, PT or T bili). Plots of PK parameters (eg, AUC_{inf} , AUC_{last} , C_{max}) versus hepatic function will be constructed, with a regression line and 90% confidence region included. Estimates of the slope and intercept, together with a 90% CI, and the coefficient of determination (ie, R-squared and adj-R-squared) may be obtained from the model.

Additionally, as an exploratory analysis, age and body weight may be explored as additional covariates/factors in the models, as appropriate.

9.3.3. Secondary Endpoint Analysis - Safety Analyses

All safety analyses will be performed on the safety population.

AEs, ECGs, BP, pulse rate, and safety laboratory data will be reviewed and summarized on an ongoing basis during the study to evaluate the safety of participants. Any clinical laboratory, ECG, BP, and pulse rate abnormalities of potential clinical concern will be described. Safety data will be presented in tabular and/or graphical format and summarized descriptively, where appropriate, following Sponsor standards.

Medical history and PE and neurological examination information, as applicable, collected during the course of the study, will be considered source data and will not be required to be reported, unless otherwise noted. However, any untoward findings identified on physical and/or neurological examinations conducted during the active collection period will be captured as AEs, if those findings meet the definition of an AE. Data collected at screening that are used for inclusion/exclusion criteria, such as laboratory data, ECGs, and vital signs, will be considered source data, and will not be required to be reported, unless otherwise noted. Demographic data collected at screening will be reported. COVID-19 specific assessments data will be considered source data and will not be required to be reported.

9.3.3.1. Electrocardiogram Analyses

Changes from baseline for the ECG parameters HR, QTcF, PR interval, and QRS complex will be summarized by treatment and time. The frequency of uncorrected QT values above 500 ms will be tabulated.

The number (%) of participants with maximum post-dose QTcF values and maximum increases from baseline in the following categories will be tabulated by treatment:

Safety QTcF Assessment

| Degree of Prolongation | Mild (ms) | Moderate (ms) | Severe (ms) |
|-------------------------------|------------------|----------------------|--------------------|
| Absolute value | >450-480 | >480-500 | >500 |
| Increase from baseline | | 30-60 | >60 |

9.3.4. Tertiary/Exploratory Endpoint(s) Analysis

9.3.4.1. Biomarkers

Biomarker data from Retained Research Samples may be collected during or after the trial and retained for future analyses; the results of such analyses are not planned to be included in the CSR.

9.3.5. Other Analyses

Pharmacogenomic data from Retained Research Samples may be collected during or after the trial and retained for future analyses; the results of such analyses are not planned to be included in the CSR.

9.4. Interim Analyses

No formal interim analysis will be conducted for this study. As this is an open-label study, the sponsor may conduct unblinded reviews of the data during the course of the study for the purpose of safety assessment, facilitating PK modeling, and/or supporting clinical development.

9.5. Sample Size Determination

A sample size of approximately 28-32 participants (approximately 8 participants per Groups 1-3, and 4-8 participants in Group 4 based on recruitment rate, with varying degrees of hepatic function in each of the 4 Groups) has been selected based on recommendation from the “FDA Guidance for Industry Pharmacokinetics in Patients with Impaired Hepatic Function: Study Design, Data Analysis, and Impact on Dosing and Labeling”. Participants who discontinue from the study before completing all assessments may be replaced at the discretion of the investigator and sponsor.

The expected widths of the 90% CIs with 80% coverage probability are shown in Table 5 for a range of possible effects (Test vs Reference). The calculation assumes the selection of the default value (80%) of the tolerance parameter in the conventional calculation.⁸ These estimates are based on an assumed conservative standard deviation of 0.6 for logAUC_{inf} (also applicable to logC_{max}) based on data from previous study C5241001 part C, fed condition.

Table 5. Expected Widths of the 90% CIs (with 80% Coverage Probability) for Different Possible Estimated Effects

| Estimated ratio 100* Test/Reference | n=8 per group | |
|--|-----------------|----------|
| | AUC | |
| | 90%CI | CI width |
| 75% | (42.73,131.64) | 88.91 |
| 100% | (56.97,175.52) | 118.55 |
| 150% | (85.46,263.28) | 177.82 |
| 200% | (113.95,351.04) | 237.09 |
| 400% | (227.89,702.08) | 474.19 |

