4. STUDY DESIGN

4.1. Overall Design

This is an open-label, single-dose, parallel-group, multicenter study to investigate the effect of varying degrees of hepatic function on the plasma PK of PF-07923568 after a single, oral **CCI** mg dose administered in the fed state (standard breakfast). Safety and tolerability will be evaluated throughout the study. A total of approximately 28-32 participants with varying degrees of hepatic function will be administered as a single, oral **CCI** mg dose of PF-07923568 in the fed state as shown in Table 3.

Table 3. Hepatic Function Categories Based on Child-Pugh Score

| Group | Description | Child-Pugh Score | Number of Participants |
|-------|-------------|---------------------------|------------------------|
| 1 | Without HI | Not Applicable | 8 ^a |
| 2 | Mild HI | Class A (5 to 6 points) | 8 |
| 3 | Moderate HI | Class B (7 to 9 points) | 8 |
| 4 | Severe HI | Class C (10 to 15 points) | 4-8 ^b |

a. Additional participants may be dosed to a maximum of 10 participants to ensure mean age ± 10 years and mean body weight ± 15 kg of this group is aligned with the pooled average assessed when approximately $\geq 75\%$ of participants are dosed across the other 3 groups.

b. The total number of participants enrolled that are classified as having severe HI will be a minimum of 4 to a maximum of 8 depending on recruitment rates.

Categorization of participants into Groups 2-4 will be done based on Child-Pugh scores determined, as described in [Appendix 10](#) at the screening visit.

Staged Enrollment of Study Groups

[figure not shown]
Participants will be dosed in a staged manner as follows:

- Participants with moderate HI (Group 3) and severe HI (Group 4) will be enrolled first.
- Recruitment of participants with mild HI (Group 2) will initiate when approximately 50% of the participants in Group 3 have been dosed.
- Sponsor approval is required before proceeding with recruitment of Group 2.*
- An average value for age and weight for the 3 HI groups (Groups 2-4) will be determined and participants without HI (Group 1) will be recruited to match the average demographics (at a minimum, age and weight, and as much as practically possible gender) across the pooled Groups 2-4.

- Recruitment for healthy participants in Group 1 (without HI) may start when approximately 75% of total participants across Groups 2-4 (ie, approximately 15 to 18 participants) have been dosed.

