## Appendix 2. SAS code

An example of the PROC MIXED code is provided below:

```
proc mixed data = tab.pk covtest alpha=0.1;
  class group;
  model l&var = group / S covb alpha=0.1 CL DDFM=KR;
  repeated/ type=un subject=subjid group=group R;
  lsmeans group;
```

```
estimate ' Mild HI vs Without HI'      group -1 1 0 0;
estimate ' Moderate HI vs Without HI" group -1 0 1 0;
estimate ' Severe HI vs Without HI"   group -1 0 0 1;
ods output lsmeans = lsmeans&var;
ods output solutionf = solution&var;
run;

/* Letter assignments for group within the estimate statement above are as follows;
A = Without HI' (Reference);
B = Mild HI (Test1)
C = Moderate HI (Test2)
D = Severe HI (Test3)
*/;
```

An example of the PROC REG code is provided below:

```
proc reg data=tab.pk;
  model l&var=clcr/clb alpha=0.1;
  ods output ParameterEstimates = param&var;
  ods output FitStatistics = fit&var;
  ods output ANOVA = reg&var;
run;
```

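### Does Table 5 need a precision figure for a severe group of fewer than 8 participants?

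*Protocol*

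**What the plan says.** Protocol section 9.5 sets the size at "approximately 8 participants per Groups 1-3, and 4-8 participants in Group 4 based on recruitment rate", 28 to 32 in total, and attributes it to an FDA guidance recommendation. It then introduces Table 5 in these words: "expected widths of the 90% CIs with 80% coverage probability are shown in Table 5 for a range of possible effects (Test vs Reference"). Only one column is given, headed for 8 per group. The inputs are printed beside it: a log-scale SD of 0.6 for AUCinf, taken to apply to Cmax as well, and the "default value (80%) of the tolerance parameter in the conventional calculation".

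The notes to Table 3 in protocol section 4.1 set the limits on group size. The severe group "will be a minimum of 4 to a maximum of 8 depending on recruitment rates". For the group without impairment, "Additional participants may be dosed to a maximum of 10 participants", for the purpose of demographic matching. SAP section 2.3 repeats both notes.

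Protocol section 9.1 and SAP section 5.1 say that no hypothesis is tested. On the analysis, protocol section 9.3.2.2 says: "A one-way ANOVA will be used to compare the natural log transformed PF-07923568" exposure parameters of each impaired group with those of the reference group, giving ratios with 90% CIs.

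**The concern.** With no test and no power calculation, Table 5 is the only quantitative statement of what the sample size delivers. It is worded for every test-versus-reference comparison but computed only for the largest permitted Group 4. The lower end of the stated total, 28, is the case of 8, 8, 8 and 4, and no precision is given for the severe comparison in that case.

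The severe comparison is also the one of most interest. Protocol section 4.2 notes that some compounds cleared in a similar way show more than a two-fold rise in exposure in severe impairment, and the results are to inform dosing recommendations. A reader who applied Table 5 to a severe group of 4 would expect too narrow an interval. At an estimated ratio of 200%, the table's lower limit is 113.95, whereas at the permitted minimum it is 99.56, just below no change.

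**Working it through.** **Inputs.** From protocol section 9.5: SD 0.6 on the natural-log scale, 90% CI, tolerance 80%, 8 in each of Groups 1-3, and 4 to 8 in Group 4. From section 4.1: up to 10 in Group 1. From section 9.3.2.2: a one-way ANOVA over four groups, so the error degrees of freedom are df = N − 4.

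**Formula.** The log half-width that the interval stays within with 80% probability is

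h = t(0.95, df) × √(χ²(0.80, df)/df) × 0.6 × √(1/n_T + 1/n_R)

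The interval at ratio R is R·exp(−h) to R·exp(h), and its width is R × (exp(h) − exp(−h)).

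**Reproducing Table 5.** With 8 vs 8 and df = 32 − 4 = 28:

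h = 1.7011 × 1.1024 × 0.6 × √(1/8 + 1/8) = 1.7011 × 1.1024 × 0.3000 = 0.5626

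At 100% this gives (56.97, 175.52), width 118.55, as printed. The other four rows also agree to two decimals. Using 14 df (two groups only) gives 127.72, and 28 df without the tolerance factor gives 106.56. Neither matches, so the printed table corresponds to the pooled four-group ANOVA with tolerance.

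**Severe comparison at the minimum.** With 4 vs 8 and df = 28 − 4 = 24:

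h = 1.7109 × 1.1097 × 0.6 × √(1/4 + 1/8) = 1.7109 × 1.1097 × 0.3674 = 0.6976

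- At 100%: (49.78, 200.89), width 151.11. Ratio to Table 5: 151.11/118.55 = 1.275.
- At 200%: (99.56, 401.77), width 302.21 against 237.09.
- Log scale: 0.6976/0.5626 = 1.24.

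**Across the permitted sizes at 100%.** The last column is the chance that the actual interval is no wider than Table 5 shows, P(χ²_df ≤ df × (0.5626/(t × SE))²), where SE = 0.6 × √(1/n_T + 1/n_R).

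| Group 1 | Group 4 | df | h | Width | Against 118.55 | Chance |
|---|---|---|---|---|---|---|
| 8 | 8 | 28 | 0.5626 | 118.55 | 0 | 80% |
| 8 | 7 | 27 | 0.5840 | 123.54 | +4.2% | 71% |
| 8 | 6 | 26 | 0.6112 | 129.99 | +9.7% | 59% |
| 8 | 5 | 25 | 0.6472 | 138.67 | +17.0% | 43% |
| 8 | 4 | 24 | 0.6976 | 151.11 | +27.5% | 26% |
| 10 | 7 | 29 | 0.5530 | 116.33 | −1.9% | 84% |
| 10 | 4 | 26 | 0.6695 | 144.13 | +21.6% | 34% |

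**Mild and moderate comparisons.** With 4 in Group 4 these remain 8 vs 8 but use 24 df: h = 0.5696, width 120.17, which is 1.4% wider than the table.

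**What depends on these widths.** The sample size is attributed to guidance. No threshold, stopping rule or enrolment trigger refers to a CI width, and the ANOVA accepts unequal group sizes.

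**The case for a change.** The strongest case for a change is that the sponsor chose to state precision and did so only for the most favourable size of the one group allowed to fall short. A column for 4 vs 8 is cheap to compute and changes nothing for participants. At the minimum, the chance that the severe interval is as narrow as the table shows is 26%, not 80%, and readers should be able to see that. All of this is arithmetically right, and an extra column would be a reasonable courtesy.

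It does not show a fault in the plan. Table 5 carries its own condition in the column heading, the range for Group 4 opens the same section, and the plan nowhere claims the tabulated precision for a smaller severe group. A statistician can compute the missing case from the printed inputs, as above. The 27.5% is also the extreme: it needs exactly 4 in Group 4 and no more than 8 in Group 1.

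A second argument is that the SAP Appendix 2 example code fits a separate variance per group ("repeated/ type=un subject=subjid group=group R"), so Table 5 might not describe the eventual analysis. That is a separate question about the example code and the ANOVA text. Nor does it simply strengthen this point. Simulation with a true SD of 0.6 in every group, and Satterthwaite degrees of freedom as an approximation to Kenward-Roger, gives a larger 80th-percentile width at 4 vs 8 (about 198). Yet the chance of an interval no wider than Table 5 rises from 26% to 31%, because a variance resting on 3 df makes the width more variable.

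**Conclusion.** No change follows. The arithmetic behind the concern holds: at the permitted minimum the severe interval is expected to be 27.5% wider than Table 5 shows (24% on the log scale), and neither document prints that figure. It is a gap in presentation that readers can fill from the stated inputs. Table 5 is correct for the size it names, no decision in the plan depends on the width, and the final report will carry the interval obtained with the group sizes actually enrolled. The loss of precision with few severe participants is an openly stated concession to recruitment.

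The sizes assume an SD of 0.6 in every group, a pooled variance across four groups, the 80% tolerance, and 8 in each of Groups 1-3. With 10 in Group 1 the excess at 4 severe participants is 21.6%, and at 7 the interval is slightly narrower than the table's. The conclusion that no change is needed does not depend on which of these sizes occurs.

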10. SUPPORTING DOCUMENTATION AND OPERATIONAL CONSIDERATIONS

10.1. Appendix 1: Regulatory, Ethical, and Study Oversight Considerations

10.1.1. Regulatory and Ethical Considerations

This study will be conducted in accordance with the protocol and with the following:

- Consensus ethical principles derived from international guidelines, including the Declaration of Helsinki and CIOMS International Ethical Guidelines;
- Applicable ICH GCP guidelines;
- Applicable laws and regulations, including applicable privacy laws.

The protocol, protocol amendments, ICD, SRSD(s), and other relevant documents (eg, advertisements) must be reviewed and approved by the sponsor, submitted to an IRB/EC by the investigator, and reviewed and approved by the IRB/EC before the study is initiated.

Any amendments to the protocol will require IRB/EC approval before implementation of changes made to the study design, except for changes necessary to eliminate an immediate hazard to study participants.

Protocols and any substantial amendments to the protocol will require health authority approval prior to initiation except for changes necessary to eliminate an immediate hazard to study participants.

The investigator will be responsible for the following:

- Providing written summaries of the status of the study to the IRB/EC annually or more frequently in accordance with the requirements, policies, and procedures established by the IRB/EC;
- Notifying the IRB/EC of SAEs or other significant safety findings as required by IRB/EC procedures;
- Providing oversight of the conduct of the study at the site and adherence to requirements of 21 CFR, ICH GCP guidelines, the IRB/EC, European regulation 536/2014 for clinical studies, European Medical Device Regulation 2017/745 for clinical device research, and all other applicable local regulations.

10.1.1.1. Reporting of Safety Issues and Serious Breaches of the Protocol or ICH GCP

In the event of any prohibition or restriction imposed (ie, clinical hold) by an applicable regulatory authority in any area of the world, or if the investigator is aware of any new information that might influence the evaluation of the benefits and risks of the study intervention, Pfizer should be informed immediately.

In addition, the investigator will inform Pfizer immediately of any urgent safety measures taken by the investigator to protect the study participants against any immediate hazard, and of any serious breaches of this protocol or of the ICH GCP guidelines that the investigator becomes aware of.

10.1.2. Financial Disclosure

Investigators and sub-investigators will provide the sponsor with sufficient, accurate financial information as requested to allow the sponsor to submit complete and accurate financial certification or disclosure statements to the appropriate regulatory authorities. Investigators are responsible for providing information on financial interests during the course of the study and for 1 year after completion of the study.

10.1.3. Informed Consent Process

The investigator or the investigator's representative will explain the nature of the study, including the risks and benefits, to the participant and answer all questions regarding the study. The participant should be given sufficient time and opportunity to ask questions and to decide whether or not to participate in the trial.

Participants must be informed that their participation is voluntary. Participants will be required to sign a statement of informed consent that meets the requirements of 21 CFR 50, local regulations, ICH guidelines, privacy and data protection requirements, where applicable, and the IRB/EC or study center.

The investigator must ensure that each participant is fully informed about the nature and objectives of the study, the sharing of data related to the study, and possible risks associated with participation, including the risks associated with the processing of the participant's personal data.

The participant must be informed that their personal study-related data will be used by the sponsor in accordance with local data protection law. The level of disclosure must also be explained to the participant.

The participant must be informed that their medical records may be examined by Clinical Quality Assurance auditors or other authorized personnel appointed by the sponsor, by appropriate IRB/EC members, and by inspectors from regulatory authorities.

The investigator further must ensure that each study participant is fully informed about their right to access and correct their personal data and to withdraw consent for the processing of their personal data.

The medical record must include a statement that written informed consent was obtained before the participant was enrolled in the study and the date on which the written consent was obtained. The authorized person obtaining the informed consent must also sign the ICD.

Participants must be reconsented to the most current version of the IRB/EC-approved ICD(s) during their participation in the study as required per local regulations.

A copy of the ICD(s) must be provided to the participant.

Participants who are rescreened are required to sign a new ICD.

